#### **4.5.5 Treatment Discontinuation Criteria**

For all subjects, global deterioration of health status requiring discontinuation of treatment without objective evidence of disease progression at that time will be captured on the health outcomes questionnaires. Tumor assessments for subjects who discontinue study treatment without radiographic progression should continue as per protocol until radiographic progression is determined.

#### **4.5.5.1 Nivolumab Dose Discontinuation**

Treatment with nivolumab should be permanently discontinued for any of the following:

- Any Grade 2 drug-related uveitis or eye pain or blurred vision that does not respond to topical therapy and does not improve to Grade 1 severity within the re-treatment period OR requires systemic treatment
- Any Grade 3 non-skin, drug-related AE lasting > 7 days, or recurs with the following exceptions for laboratory abnormalities, diarrhea, colitis, neurologic toxicity, drug-related uveitis, pneumonitis, bronchospasm, hypersensitivity reactions, infusion reactions, and endocrinopathies:
  - Grade 3 drug-related diarrhea, colitis, neurologic toxicity, myocarditis, uveitis, pneumonitis, bronchospasm, hypersensitivity reaction, or infusion reaction of any duration requires discontinuation
  - Grade 3 drug-related endocrinopathies, adequately controlled with only physiologic hormone replacement do not require discontinuation. Adrenal insufficiency requires discontinuation regardless of control with hormone replacement.
  - Grade 3 drug-related laboratory abnormalities do not require treatment discontinuation except:
    - Grade 3 drug-related thrombocytopenia > 7 days or associated with bleeding requires discontinuation
    - Any drug-related liver function test (LFT) abnormality that meets the following criteria require discontinuation:
      - Grade  $\geq 3$  drug-related AST, ALT or Total Bilirubin requires discontinuation\*
      - Concurrent AST or ALT > 3 x ULN and total bilirubin > 2x ULN
  - \* In most cases of Grade 3 AST or ALT elevation, study treatment will be permanently discontinued. If the investigator determines a possible favorable benefit/risk ratio that warrants continuation of study treatment, a discussion between the investigator and the BMS Medical Monitor/designee must occur.
- Any Grade 4 drug-related adverse event or laboratory abnormality (including but not limited to creatinine, AST, ALT, or Total Bilirubin), except for the following events, which do not require discontinuation:
  - Grade 4 neutropenia  $\leq 7$  days
  - Grade 4 lymphopenia or leukopenia or asymptomatic amylase or lipase
  - Isolated Grade 4 electrolyte imbalances/abnormalities that are not associated with clinical sequelae and are corrected with supplementation/appropriate management within 72 hours of their onset
  - Grade 4 drug-related endocrinopathy adverse events, such as, hyper- or hypothyroidism, or glucose intolerance, which resolve or are adequately controlled with physiologic hormone replacement (corticosteroids, thyroid hormones) or glucose-controlling agents, respectively, may not require discontinuation after discussion with and approval from the BMS Medical Monitor.

- Any event that leads to delay in dosing lasting > 6 weeks from the previous dose requires discontinuation, with the following exceptions:
  - Dosing delays to allow for prolonged steroid tapers to manage drug-related adverse events are allowed.
  - Dosing delays lasting > 6 weeks from the previous dose that occur for non-drug-related reasons may be allowed if approved by the BMS Medical Monitor (or designee).
- Any adverse event, laboratory abnormality, or intercurrent illness which, in the judgment of the Investigator, presents a substantial clinical risk to the subject with continued nivolumab dosing.

Prior to re-initiating treatment in a participant with a dosing delay lasting > 6 weeks, the BMS Medical Monitor (or designee) must be consulted. Tumor assessments should continue as per protocol even if dosing is delayed. Periodic study visits to assess safety and laboratory studies should also continue every 6 weeks or more frequently if clinically indicated during such dosing delays.

The assessment for discontinuation of nivolumab should be made separately from the assessment made for discontinuation of ipilimumab or ipilimumab-placebo. Although there is overlap among the discontinuation criteria, if discontinuation criteria are met for ipilimumab but not for nivolumab, treatment with nivolumab may continue if ipilimumab or ipilimumab-placebo is discontinued.

If a subject meets criteria for discontinuation and investigator is unable to determine whether the event is related to both or one study drug, the subject should discontinue both nivolumab and ipilimumab or ipilimumab-placebo and be taken off the treatment phase of the study. Continuation of ipilimumab or ipilimumab-placebo after discontinuation of nivolumab is not allowed on study.

#### **4.5.5.2 *Ipilimumab/ipilimumab-placebo Dose Discontinuation***

Ipilimumab or ipilimumab-placebo should be permanently discontinued if any of the following criteria are met:

- Any Grade  $\geq 2$  drug-related uveitis or eye pain or blurred vision that does not respond to topical therapy and does not improve to Grade 1 severity within 2 weeks OR requires systemic treatment;
- Any Grade  $\geq 3$  bronchospasm or other hypersensitivity reaction;
- Any other Grade 3 non-skin, drug-related adverse event with the following exceptions for laboratory abnormalities, grade 3 nausea and vomiting, grade 3 neutropenia and thrombocytopenia, and symptomatic endocrinopathies which resolved (with or without hormone substitution);
- Any drug-related liver function test (LFT) abnormality that meets the following criteria require discontinuation:
  - AST or ALT > 8 x ULN
  - Total bilirubin > 5 x ULN
  - Concurrent AST or ALT > 3 x ULN and total bilirubin > 2 x ULN

- Any Grade 4 drug-related adverse event or laboratory abnormality, except for the following events, which do not require discontinuation:
  - Grade 4 neutropenia  $\leq 7$  days
  - Grade 4 lymphopenia or leukopenia
  - Isolated Grade 4 amylase or lipase abnormalities which are not associated with symptoms or clinical manifestations of pancreatitis. The BMS Medical Monitor should be consulted for Grade 4 amylase or lipase abnormalities.
  - Isolated Grade 4 electrolyte imbalances/abnormalities that are not associated with clinical sequelae and are corrected with supplementation/appropriate management within 72 hours of their onset
- Any treatment delay resulting in no ipilimumab or ipilimumab-placebo dosing for  $> 12$  weeks with the following exceptions: Dosing delays to manage drug-related adverse events, such as prolonged steroid tapers, are allowed. Prior to re-initiating treatment in a subject with a dosing delay lasting  $> 12$  weeks, the BMS medical monitor must be consulted. Tumor assessments should continue as per protocol even if dosing is delayed.
- Dosing delays resulting in no ipilimumab or ipilimumab-placebo dosing for  $> 12$  weeks that occur for non-drug-related reasons may be allowed if approved by the BMS medical monitor. Prior to re-initiating treatment in a subject with a dosing delay lasting  $> 12$  weeks, the BMS medical monitor must be consulted. Tumor assessments should continue as per protocol even if dosing is delayed.
- Any adverse event, laboratory abnormality, or intercurrent illness which, in the judgment of the Investigator, presents a substantial clinical risk to the subject with continued ipilimumab or ipilimumab-placebo dosing.

The assessment for discontinuation of ipilimumab or ipilimumab-placebo should be made separately from the assessment made for discontinuation of nivolumab. Although there is overlap among the discontinuation criteria, if discontinuation criteria are met for ipilimumab or ipilimumab-placebo but not for nivolumab, treatment with nivolumab may continue if ipilimumab or ipilimumab-placebo is discontinued.

If a subject meets criteria for discontinuation and investigator is unable to determine whether the event is related to both or one study drug, the subject should discontinue both nivolumab and ipilimumab or ipilimumab-placebo and be taken off the treatment phase of the study.

#### **4.5.6 Management Algorithms for Immuno-Oncology Agents**

Immuno-oncology (I-O) agents are associated with AEs that can differ in severity and duration than AEs caused by other therapeutic classes. Nivolumab and ipilimumab are considered immuno-oncology agents in this protocol. Early recognition and management of AEs associated with immuno-oncology agents may mitigate severe toxicity. Management Algorithms have been developed to assist investigators in assessing and managing the following groups of AEs:

- Gastrointestinal
- Renal
- Pulmonary
- Hepatic
- Endocrinopathy
- Skin

- Neurological

The above algorithms are found in both the nivolumab and ipilimumab Investigator Brochures, as well as in [Appendix 2](#).

#### **4.5.6.1 Treatment Beyond Disease Progression**

Accumulating evidence indicates a minority of subjects treated with immunotherapy may derive clinical benefit despite initial evidence of progression of disease (PD).

Subjects will be permitted to continue on nivolumab + ipilimumab or ipilimumab-placebo for treatment beyond initial RECIST 1.1 defined PD, assessed by the investigator for up to a maximum of 24 months from the date of the first dose as long as they meet the following criteria:

- Investigator-assessed clinical benefit and no rapid disease progression
- Tolerance of study drug
- Stable performance status
- Treatment beyond progression will not delay an imminent intervention to prevent serious complications of disease progression (eg, CNS metastases)
- Subject provides written informed consent prior to receiving additional nivolumab and ipilimumab or ipilimumab-placebo treatment, using an ICF describing any reasonably foreseeable risks or discomforts, or other alternative treatment options. The decision to continue treatment beyond initial investigator-assessed progression should be discussed with the BMS Medical Monitor and documented in the study records.
- In cases where the subject is treated beyond investigator-assessed progression which is not confirmed by BICR, the subject should continue to be scanned following the study imaging schedule (every 6 weeks until week 48 and every 12 weeks thereafter). If the subject is treated beyond investigator-assessed progression that is confirmed by BICR a follow-up scan should be performed within six (6) weeks  $\pm$  5 days of original PD to determine whether there has been a decrease in the tumor size, or continued progression of disease. In this case, subsequent scans should be performed every twelve (12) weeks until further progression is determined.

If the investigator feels that the subject continues to achieve clinical benefit by continuing treatment, the subject should remain on the trial and continue to receive monitoring according to the Time and Events Schedule in [Table 5.1-1](#), [Table 5.1-2](#), and [Table 5.1-3](#).

For the subjects who continue study therapy beyond progression, further progression is defined as an additional 10% increase in tumor burden from time of initial PD. This includes an increase in the sum of diameters of all target lesions and/ or the diameters of new measurable lesions compared to the time of initial PD. Nivolumab and ipilimumab or ipilimumab-placebo treatment should be discontinued permanently upon documentation of further progression.

New lesions are considered measurable at the time of initial progression if the longest diameter is at least 10 mm (except for pathological lymph nodes which must have a short axis of at least 15 mm). Any new lesion considered non-measurable at the time of initial progression may become measurable and therefore included in the tumor burden if the longest diameter increases

to at least 10 mm (except for pathological lymph nodes which must have a short axis of at least 15 mm).

In situations where the relative increase in total tumor burden by 10% is solely due to inclusion of new lesions which become measurable, these new lesions must demonstrate an absolute increase of at least 5 mm.

#### **4.5.7 Treatment of Infusion Reactions**

##### **4.5.7.1 Nivolumab or Ipilimumab Infusion Reactions**

Since nivolumab and ipilimumab contain only human immunoglobulin protein sequences, they are unlikely to be immunogenic and induce infusion or hypersensitivity reactions. However, if such a reaction were to occur, it might manifest with fever, chills, rigors, headache, rash, pruritus, arthralgias, hypo- or hypertension, bronchospasm, or other symptoms. All Grade 3 or 4 infusion reactions should be reported within 24 hours to the BMS Medical Monitor and reported as an SAE if criteria are met. Infusion reactions should be graded according to National Institute of cancer (NCI) common terminology criteria for adverse event (CTCAE, Version 4.0) guidelines.

Treatment recommendations are provided below and may be modified based on local treatment standards and guidelines, as appropriate:

For Grade 1 symptoms: (mild reaction; infusion interruption not indicated; intervention not indicated)

- Remain at bedside and monitor subject until recovery from symptoms. The following prophylactic premedications are recommended for future infusions: diphenhydramine 50 mg (or equivalent) and/or acetaminophen/paracetamol 325 to 1000 mg at least 30 minutes before additional nivolumab or ipilimumab or ipilimumab-placebo administrations.

For Grade 2 symptoms: (moderate reaction requires therapy or infusion interruption but responds promptly to symptomatic treatment [eg, antihistamines, non-steroidal anti-inflammatory drugs, narcotics, corticosteroids, bronchodilators, IV fluids]; prophylactic medications indicated for ≤ 24 hours)

- Stop the nivolumab or ipilimumab or ipilimumab-placebo infusion, begin an IV infusion of normal saline, and treat the subject with diphenhydramine 50 mg IV (or equivalent) and/or acetaminophen/paracetamol 325 to 1000 mg; remain at bedside and monitor subject until resolution of symptoms. Corticosteroid and/or bronchodilator therapy may also be administered as appropriate. If the infusion is interrupted, then restart the infusion at 50% of the original infusion rate when symptoms resolve; if no further complications ensue after 30 minutes, the rate may be increased to 100% of the original infusion rate. Monitor subject closely. If symptoms recur, then no further nivolumab or ipilimumab or ipilimumab-placebo will be administered at that visit. Administer diphenhydramine 50 mg IV, and remain at bedside and monitor the subject until resolution of symptoms. The amount of study drug infused must be recorded on the electronic case report form (eCRF).
- For future infusions, the following prophylactic premedications are recommended: diphenhydramine 50 mg (or equivalent) and/or acetaminophen/paracetamol 325 to 1000 mg

should be administered at least 30 minutes before nivolumab or ipilimumab or ipilimumab-placebo infusions. If necessary, corticosteroids (up to 25 mg of SoluCortef or equivalent) may be used.

For Grade 3 or 4 symptoms: (severe reaction, Grade 3: prolonged [ie, not rapidly responsive to symptomatic medication and/or brief interruption of infusion]; recurrence of symptoms following initial improvement; hospitalization indicated for other clinical sequelae [eg, renal impairment, pulmonary infiltrates]. Grade 4: Life threatening; pressor or ventilatory support indicated).

- Immediately discontinue infusion of nivolumab or ipilimumab or ipilimumab-placebo. Begin an IV infusion of normal saline and treat the subject as follows: Recommend bronchodilators, epinephrine 0.2 to 1 mg of a 1:1000 solution for subcutaneous administration or 0.1 to 0.25 mg of a 1:10,000 solution injected slowly for IV administration, and/or diphenhydramine 50 mg IV with methylprednisolone 100 mg IV (or equivalent), as needed. Subject should be monitored until the investigator is comfortable that the symptoms will not recur. Nivolumab or ipilimumab or ipilimumab-placebo will be permanently discontinued. Investigators should follow their institutional guidelines for the treatment of anaphylaxis. Remain at bedside and monitor subject until recovery of the symptoms.

In case of late-occurring hypersensitivity symptoms (eg, appearance of a localized or generalized pruritus within 1 week after treatment), symptomatic treatment may be given (eg, oral antihistamine or corticosteroids).

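### An infusion reaction that returns after the infusion is restarted fits both the Grade 2 instruction (stop for that visit) and the Grade 3 definition (stop permanently)

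*Protocol*

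**What the plan says.** Protocol section 4.5.7.1 sets out the handling of infusion reactions by grade.

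- **Grade 2, definition:** "moderate reaction requires therapy or infusion interruption but responds promptly to symptomatic treatment". Recurrence is not mentioned.
- **Grade 2, action:** if the infusion was interrupted, "restart the infusion at 50% of the original infusion rate when symptoms resolve". For a recurrence: "If symptoms recur, then no further nivolumab or ipilimumab or ipilimumab-placebo will be administered at that visit".
- **Grade 2, later visits:** a separate bullet begins "For future infusions, the following prophylactic premedications are recommended".
- **Grade 3, definition:** the listed features include "recurrence of symptoms following initial improvement; hospitalization indicated for other clinical sequelae".
- **Grade 3 or 4, action:** "Nivolumab or ipilimumab or ipilimumab-placebo will be permanently discontinued".
- **Reporting:** "All Grade 3 or 4 infusion reactions should be reported within 24 hours to the BMS Medical Monitor". This sentence does not cover Grade 2.

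Section 4.5.5.1 (nivolumab) says of Grade 3 drug-related events: "hypersensitivity reaction, or infusion reaction of any duration requires discontinuation". It also bars ipilimumab or its placebo once nivolumab has been discontinued. Section 4.5.5.2 stops ipilimumab or placebo for other Grade 3 non-skin drug-related events, and infusion reactions are not among its exceptions.

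**The concern.** The Grade 2 instruction and the Grade 3 definition cover the same event but dispose of it differently. A site working from the Grade 2 bullet stops dosing for the day and may plan the next infusion with premedication. A site working from the Grade 3 definition stops the drug permanently and notifies the Medical Monitor within 24 hours. If the drug is nivolumab, stopping it ends all study treatment.

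The main stake is the safety and treatment of the individual subject. There is also a data consequence. Protocol sections 8.4 and 8.4.3 plan tables of AEs by worst grade and of AEs leading to discontinuation, and a recurrence would enter them differently depending on which sentence the site followed. Nivolumab is given in both arms, so subjects in either arm can be affected.

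**Working it through.** The plan has no figure to reproduce here. The check is a comparison of the passages.

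**Step 1: do the two descriptions overlap?** Under the Grade 2 bullet, the infusion restarts only after symptoms have resolved. Symptoms that return after restart have therefore improved first. That is the recurrence criterion in the Grade 3 definition, so on the plain wording every event covered by the Grade 2 recurrence sentence also fits the Grade 3 description.

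**Step 2: what follows from each grade?**

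| | Treated as Grade 2 | Treated as Grade 3 |
|---|---|---|
| At the visit (4.5.7.1) | No more drug at that visit | Infusion stopped at once |
| Later dosing (4.5.7.1) | Later infusions foreseen, with premedication | Permanent discontinuation |
| Delay and resume rules (4.5.2.1, 4.5.4.1, 4.5.4.2) | Delay for a Grade 2 non-skin drug-related AE; dosing may resume at Grade 1 or baseline | Not reached |
| Discontinuation rules (4.5.5.1, 4.5.5.2) | Not triggered by the grade alone | Triggered for a drug-related reaction |
| 24-hour notice to the Medical Monitor (4.5.7.1) | Not required by that sentence | Required |

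The Grade 2 route to later dosing therefore rests on the general delay and resume rules as well as on the limit to one visit.

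**Step 3: does any text settle which applies?** Two sentences in 4.5.7.1 might.

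- Infusion reactions are to be graded by CTCAE version 4.0. This does not withdraw the separate instruction for recurrence printed under Grade 2.
- The treatment recommendations may be adapted to local standards. This does not assign a grade to a recurrence, and 4.5.5.1 and 4.5.5.2 state their Grade 3 rules without any such allowance.

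Neither resolves the overlap.

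**Step 4: how many subjects?** The documents give no rate of infusion reactions or of recurrence. Both rates below are assumptions, applied to the planned 396 subjects.

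- Grade 2 reaction in 1% to 5%: 0.01 × 396 = 3.96 and 0.05 × 396 = 19.8, or about 4 to 20 subjects.
- Recurrence in 10% to 30% of these: 0.10 × 3.96 = 0.4 and 0.30 × 19.8 = 5.9, or about 0 to 6 subjects.
- Upper end as a share of the trial: 6 / 396 = 1.5%.

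**The case against.** The strongest reply is that both instructions can be obeyed. Stopping drug at that visit is a bedside step, and permanent discontinuation is a later decision that depends on grade. Recurrence appears in only one grade definition, Grade 3; under Grade 2 it appears only as an action. On this reading the event starts as Grade 2, is re-graded when symptoms return, and the drug is then discontinued. The premedication bullet serves all Grade 2 subjects, and nothing expressly orders re-dosing after a recurrence.

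Part of this stands. Re-treatment is implied, not written. The line in 4.5.5.1 applies to Grade 3 drug-related reactions and adds no definition of recurrence of its own. The acute treatments overlap: both bullets use saline and diphenhydramine, both allow corticosteroids and bronchodilators, and the Grade 3 or 4 measures are given as needed. The number affected is small and may be zero, and no effect on the primary ORR comparison has been shown.

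The re-grading sequence itself, however, is not written in the protocol. If every recurrence were Grade 3, an instruction limited to one visit would have no reason to stand under Grade 2. A site that keeps the event at Grade 2 is following printed text, is supported by the delay and resume rules, and is not prompted by the 24-hour sentence to consult the Medical Monitor.

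**Conclusion.** The concern holds. It is an internal contradiction in section 4.5.7.1 that carries into 4.5.5.1 and 4.5.5.2: a recurrence after restart has two possible grades and two dispositions, and no visible text chooses between them. This follows from the wording alone and does not depend on any assumed rate.

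The size does depend on assumption: about 0 to 6 of 396 subjects under the ranges shown. For each, one AE grade, one 24-hour report and the remaining treatment (24 months from first dose is the protocol maximum, not an expected loss) turn on which sentence the site follows. The effect on summary safety tables is therefore likely to be small. The case for correction rests on subject safety and consistent handling between sites. It should be corrected, but it does not threaten the primary analysis.

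**What to change.** Reconcile the Grade 2 recurrence sentence and the Grade 3 definition in 4.5.7.1 with 4.5.5.1 and 4.5.5.2, so that a recurrence after restart carries one grade and one instruction, either for that visit only or permanent. The Grade 2 instruction and the Grade 3 definition should not both cover it. Use the same grade on the AE page and for the 24-hour notice. Which rule applies is for the sponsor to decide; this review takes no position on it.

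The cost is one or two sentences in the next protocol revision, with no extra procedures or patients.
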